11.1 Final Analysis Plan

Data to be collected includes:

Item	Type of Variable
Willingness to Participate 
• Dentist, Hygienist, Assistant and Front Desk personnel willing to participate• Patient willingness to participate	
• Willingness to participate (Binary – Yes/No)
Triage Survey	
• Ease of Administration (3 point Likert Scale)
◦ Very easy to complete survey due to administration method◦ Easy to administer complete survey due to administration method◦ Not easy to complete survey due to survey administration method• Completeness (Binary – Yes/No)• Question understandability (3 point Likert Scale)
◦ Very clear to understand◦ Understandable with some clarification provided by the administrator◦ Not clear to understand
Safety Perception Survey 
• Start-of-Study DHCW Survey• End-of-Study DHCW Survey• Start-of-Visit Patient Survey• End-of-Visit Patient Survey	
• Administration method (3 point Likert Scale)
◦ Very easy to complete survey due to administration method◦ Easy to complete survey due to administration method◦ Not easy to complete survey due to administration method• Completeness (Binary – Yes/No)• Question understandability (3 point Likert Scale)
◦ Very clear to understand◦ Understandable with some clarification provided by the administrator◦ Not clear to understand
Testing Logistics 
• LAB – saliva SARS-CoV-2 viral test• POC – BD Veritor COVID-19 antigen test• PCR viral SARS-CoV-2 test• ELISA antibody SARS-CoV-2 test	
• Specimen Collection (3 point Likert Scale)
◦ Very easy to collect◦ Easy to collect◦ Not easy to collect• Specimen preparation for shipping (3 point Likert Scale)
◦ Very easy to prepare◦ Easy to prepare◦ Not easy to prepare• Specimen storage (Binary – Easy/Not Easy)
◦ Easy to Store◦ Not easy to store• Timeliness of results (3 point Likert Scale)
◦ Very timeless access to results◦ Timely access to results◦ Access to results not timely• Reporting of results (3 point Likert Scale)
◦ Very easy to access results◦ Easy to access results◦ Not easy to access results
Testing Case Report	
• Completeness (Binary – Yes/No)

Descriptive statistics (frequencies) for all variables will be performed.

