
To Determine Ease of Use with REDCap Survey Instruments
 
 • Dental Health Care Worker Subject 
 ◦ Start-of-Study Survey ◦ End-of-Study Survey ◦ Triage Survey • Patient Subject 
 ◦ Start-of-Visit Survey ◦ End-of-Visit Survey ◦ Triage Survey 	Determining the ease of use and completeness of the REDCap instruments enables refinement of the system	
For both DHCW and Patients
 
 • % who feel surveys are easy to complete due to administration method: 
 ◦ Start-of-Study DHCW Survey ◦ End-of-Study DHCW Survey ◦ Pre-Visit Patient Survey ◦ End-of-Visit Patient Survey ◦ Triage Case Report • % who feel survey questions were understandable: 
 ◦ Start-of-Study DHCW Survey ◦ End-of-Study DHCW Survey ◦ Pre-Visit Patient Survey ◦ End-of-Visit Patient Survey ◦ Triage Case Report • % completed surveys: 
 ◦ Start-of-Study DHCW Survey ◦ End-of-Study DHCW Survey ◦ Pre-Visit Patient Survey ◦ End-of-Visit Patient Survey ◦ Triage Case Report 	
% indicating surveys were easy to complete due to administration method:
 
 • For DHCW - At time End-of-Study (Day 28) • Patients – End-Of-Visit (Day 1) 
% indicating survey questions were easy to understand:
 
 • For DHCW - At time End-of-Study (Day 28) • Patients – End-Of-Visit (Day 1) 
% Surveys Completed:
 
 • For DHCW - At time End-of-Study (Day 28) • Patients – End-Of-Visit (Day 1)

3.1 Primary Outcomes for Full Study (Data Collection is Being Performed to Determine Instrument Feasibility)

Full Study Objective	Brief Description/Justification of Outcome Measure	Outcome Measured By	Time Frame

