7.1 Study Procedures/Evaluations

The following study procedures will be completed

Group 1- DHCW Subjects in POC Offices

Procedure and Evaluations	Purpose	Completed as Part of Study	When Completed	Who Completes
Complete Consent	Complete informed consent	Yes	Prior to Enrollment	Study investigators meet with subjects and document consent in REDCap
Start-of-study DHCW Survey 
• PPE used• Environmental Controls Used• Perception of Importance• Comfort• Safety• COVID-19 Testing Preferences• Vaccination Opinions	Collect baseline Outcomes measures	Yes	Start-of-Study (day 0)	Data entered via REDCap self-administered survey
Triage Case Reports	Collect COVID-19 screening data	Yes	Start-of-Study (Day 0) Mid-Study (Day 14) End of Study (Day 28)	Data entered into REDCap via eCRF by the Practitioner
Testing Case Reports	Collect information on outcomes of COVID-19 testing	Yes	Start-of-Study (Day 0) Mid-Study (Day 14) End of Study (Day 28)	POC Test POC SARS-CoV-2 antigen test results entered into REDCap by the Practitioner or designated investigator for all DHCWs ELISA Ab test For Practitioner- Data entered into REDCap eCRF by the PI and/or Chief Clinical Officer For other DHCWs- Data entered into REDCap eCRF by the PI and/or Chief Clinical Officer
End-of-Study DHCW Survey	Collect payment information	Yes	End-of-Study (Day 28)	Data entered via REDCap self-administered survey.
Dental Health Care Participation Questionnaire	Collect feasibility information on surveys and logistics	Yes	End-of-Study (Day 28)	Data entered via REDCap self-administered survey.

Group 2- Patient Subjects in POC Offices

Procedure and Evaluations	Purpose	Completed as Part of Study	When Performed	How Completed
Obtain Informed Consent	Complete informed consent	Yes	2 Weeks Prior (day -14 +/-14 days)	Electronic consent and signatures obtained prior to initiating Pre-Visit Patient Survey
Patient Start-of-Visit Survey • Safety and Comfort • COVID-19 Testing Preferences • Perception of Importance • Medical history Likelihood to report COVID-19 symptoms	Collect outcome measures	Yes	2 Weeks Prior (day -14 +/- 14 days)	Data entered via REDCap self-administered survey.
Triage Case Report	Collect COVID-19 screening data	Yes	Visit (day 1)	Data entered into REDCap via eCRF by the Practitioner or their investigator designee

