7.2.2 Specimen Preparation, Handling, and Storage

The following details specimen preparation, handling and storage.

	POC Test	PCR Viral Test	ELISA Antibody Test
Sample Collection & Shipping			
Sample Collection Materials	Nasal swab included in BD Veritor or Abbott COVID-19 antigen card system	Saliva collection kit via Spectrum and/or Tongue cell collection kit via Oral Biology Laboratory	Capillary blood sample via Mitra Cartridge
Storage of Specimen Collection Supplies and Test Kits	National Dental PBRN Office after kits are mail to them from the Clinical Research Center at the Rutgers School of Dental Medicine	National Dental PBRN Office after kits are mail to them from the Clinical Research Center at the Rutgers School of Dental Medicine	National Dental PBRN Office after kits are mail to them from the Clinical Research Center at the Rutgers School of Dental Medicine

Transport Media	Not applicable (POC Test)	Buffer solution	Sponge with capillary blood is transported with desiccant
Packaging Specimen for Shipping	Not applicable (POC Test)	Sealed biohazard plastic bag placed into a 95 kPa bio-hazard bag with absorbent which is placed into a UN3373 Category B certified box.	Post sampling, the closed Mitra Cartridge is inserted into sealed specimen bag which contains a desiccant that absorbs moisture, and inserted in a shipping UN3373 Category B certified box.
Sample Processing (Performing the Test)			
Processing Supplies	Included in point-of-care BD Veritor or Abbott COVID-19 antigen card	RNA extraction, followed by RT-PCR	96 well plate, ELISA reagents
Processing Time	15 minutes	About four hours	Overnight extraction at 4C, followed by automated ELISA
Conditions for Stability and Transport Condition			
Stability prior to Use	No special storage conditions required	No special storage conditions required	No special storage conditions required Dry blood on Mitra Cartridge stable at room temperature for 28 days.
Stability during shipping	Not applicable (POC Test)	Yes due to transport media	Yes due to desiccant
Storage prior to processing	Not applicable (POC Test)	Oral Biology Laboratory and/or Genomics Laboratory	PHRI Laboratory
Stability prior to processing	Stable at room temperature	Stable at room temperature	Stable at room temperature
Tracking			
Labeling	Not applicable (POC Test)	Specimen ID (bar code) Subject ID (bar code) Subject Name Date of Specimen	Specimen ID (bar code) Subject ID (bar code) Subject Name Date of Specimen

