As this is a feasibility study, reviews of surveys and case reports to ensure completeness will not be completed, rather the number/percentage of incomplete surveys and forms will be analyzed as an outcome measure. Consent forms will be reviewed for completeness at the mid-study visit for DHCW subjects and as part of the end-of-visit survey for patient subjects.

Data Management Controls

REDCap is a rich system which enables privileging, required data element entry and required data validation to be embedded into daily operations.

- **Privileging:** Every study staff member will be assigned a role which carries specific read/write/edit/delete privileges. Staff member will be assigned a role providing minimal rights sufficient to perform his/her responsibilities.
- **Structured Data:** Whenever possible, data will be collected via structured data responses rather than free-text. Structured data requires a respondent to check a valid response.
- **Data Validation:** Data fields will be established limiting responses to those that are reasonable. For example, year of birth would have a range of 2002 (corresponding to age 18 – the youngest

eligible) to 1920 (corresponding to age 100 – more than sufficient to cover the age range of individuals having impacted 3rd molars extracted.)

- **Required Fields:** Whenever appropriate, fields have been made required so as to ensure completed forms and questionnaires.

Structured responses are required for the CRFs so only valid responses can be recorded. In addition, REDCap has been programmed with all responses being required at time of completion which will trigger an error message, but subjects can save their responses without all responses being completed. Validation rules are employed where possible.

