15.2 Data Capture Methods

Other than the Testing Case Report, all data for the study be electronically captured. Various devices will be used including:

- Laptop and desktop computers to complete surveys and forms directly into REDCap, the electronic data capture system for the study
- iPads to complete surveys, forms and capture electronic signatures directly into REDCap
- Bar code scanner to label study specimens

Patients will use their own computer or personal electronic device to sign the consent form and answer the pre-visit survey. DHCW will use their own computer, electronic device, an office computer electronic device or the study provided electronic pads for consents. All other forms and surveys to be completed DHCW or patient subjects by using study provided electronic pads.

REDCap will be used to collect and maintain all study data.

	DHCW Method of Collection	DHCW Entered By Whom	PATIENTS Method of Collection	PATIENTS Entered by Whom
Surveys	Survey administered via REDCap with responses entered directly into REDCap	By study participant on office iPad	Survey administered via REDCap with responses entered directly into REDCap	By study participant on computer or other electronic device at home
Triage Survey Case Report	Survey administered via REDCap form with responses entered directly into REDCap	By PBRN Practitioner or Investigator designee	REDCap form	By PBRN Practitioner or Investigator designee
POC Test Results Case Report	Data from Veritor Reader or Abbott COVID-19 Ag Card	By PBRN Practitioner or Investigator designee	Data from Veritor Reader or Abbott COVID-19 Ag Card	By PBRN Practitioner or Investigator designee
PCR Test Results Case Report	Data entered directly of e-mail of results into REDCap Form upon receipt of secure e-mail from lab	Rutgers PI, Chief of Protocol or Designee	Data entered directly into REDCap Form upon receipt of secure e-mail from lab	Rutgers PI, Chief of Protocol or Designee
ELISA Antibody Test Results Case Report	Data entered directly from e-mail of results into REDCap Form upon receipt of secure e-mail from lab	Rutgers PI, Chief of Protocol or Designee	Data entered directly into REDCap Form upon receipt of secure e-mail from lab	Rutgers PI, Chief of Protocol or Designee

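### Two response scales in section 11.1 do not fit what they rate: POC shipping and storage have no not-applicable category, and self-administered surveys get a middle option that needs an administrator

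*Combined protocol and SAP*

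**What the plan says.** **Shipping and storage.** The Testing Logistics row of section 11.1 names four tests, including "POC – BD Veritor COVID-19 antigen test", against one common set of five items. One is "Specimen preparation for shipping (3 point Likert Scale"), with options from very easy to not easy. Another is specimen storage, rated easy or not easy. Neither has a not-applicable category, and the only stated analysis is frequencies for all variables. Section 3.0 uses these ratings in a feasibility outcome, the percentage who found the testing procedure easy to comply with, and names POC there. In section 7.2.2 the POC entries for packaging for shipping and for storage before processing both read "Not applicable (POC Test").

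**Understandability.** Section 11.1 gives the Triage Survey and the four perception surveys the same three options. The middle one is "Understandable with some clarification provided by the administrator". Section 7.1 describes the perception surveys as self-administered. The table in section 15.2 has patients completing surveys "By study participant on computer or other electronic device at home". The text of 15.2 limits patients' own devices to the consent and the pre-visit survey and puts the other surveys on study-provided pads.

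**Triage Case Report.** Section 3.0 takes the percentage "who feel surveys are easy to complete due to administration method" from both DHCWs and patients, and includes the Triage Case Report. Section 7.1 says of that form, for DHCWs in POC offices, "Data entered into REDCap via eCRF by the Practitioner". Other groups have similar entries, by the practitioner, a designee or central study staff.

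**The concern.** A rating is informative only if the respondent performed or experienced the step. A patient in a POC office has one nasal swab, taken and processed by the practitioner or a designee, and no other study specimen. Asked how easy it was to prepare that specimen for shipping or to store it, the patient can give an arbitrary answer or leave a blank. Section 13 adds pressure to answer: "REDCap has been programmed with all responses being required at time of completion which will trigger an error message", although it also lets subjects save an incomplete form.

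The understandability scale has a different fault. Someone who hesitated over a question but worked it out alone is neither wholly clear nor unclear, and the only option between those two describes help from a person who, for a self-administered survey, is not part of the procedure.

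The purpose of the study is to refine procedures and instruments for a larger application, and its results are frequencies. Response options and denominators therefore determine what it reports, and they are hard to repair once the data are in.

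**Working it through.** The documents state no ease or understandability percentage, so there is no figure to reproduce. The enrolment caps agree with each other: 4 offices × 10 = 40 DHCWs and 4 × 20 = 80 patients.

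**Step 1: who has a specimen to ship or store.** From the protocol summary and sections 5.3 and 7, at the caps:

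- POC patients: 2 offices × 20 = 40. Antigen swab only, nothing shipped.
- LAB patients: 2 × 20 = 40. Saliva kit, packaged and dropped off by the patient.
- POC DHCWs: 2 × 10 = 20. The antigen test is not shipped, but the finger-prick cartridge for ELISA is packaged for shipment.
- LAB DHCWs: 2 × 10 = 20. PCR specimen(s) and ELISA cartridge, both shipped.

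Only POC patients have no shipped specimen at all. POC DHCWs have a real shipping step for ELISA, though not for the antigen test.

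**Step 2: results reported by test.** The LAB, PCR and ELISA percentages are unaffected. The POC shipping and storage percentages describe steps that 7.2.2 says do not apply.

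**Step 3: results pooled across tests.** The plan does not say whether it will pool; assume it does. Let p be the true proportion easy where the item applies, and a the share of not-applicable ratings recorded as easy. A blank kept in the denominator counts as a = 0.

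Reported proportion = (p × n_applicable + a × n_not applicable) / (n_applicable + n_not applicable)

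Patients, 40 applicable and 40 not:

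| Assumed true p | a = 0 | a = 1 |
|---|---|---|
| 50% | 20/80 = 25% | 60/80 = 75% |
| 70% | 28/80 = 35% | 68/80 = 85% |
| 90% | 36/80 = 45% | 76/80 = 95% |

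DHCW viral or antigen ratings, 20 applicable and 20 not, give the same ranges. Adding the 40 ELISA ratings makes 60 applicable and 20 not: a true 70% is then reported as 42/80 = 52.5% to 62/80 = 77.5%. These are extremes under assumed values of p and a, not predictions.

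**Step 4: the middle understandability option, by instrument.**

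- Triage Survey: the practitioner or designee administers it (15.2), so the wording fits.
- Pre-visit patient survey: it launches automatically after electronic consent (section 7) and is done on the patient's own device (15.2). No administrator is present, so the wording does not fit.
- End-of-visit patient survey and DHCW surveys: self-administered under 7.1, but staff may be nearby. The misfit is real but weaker, and for the end-of-visit survey it depends on which part of 15.2 applies.

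**Step 5: the Triage Case Report.** The respondent hears and answers the symptom questions, so can rate whether they were clear. The person entering the form is the one who knows how easy it was to administer. Section 11.1 labels this item as ease of administration, while section 3.0 takes the ease rating from DHCWs and patients in general.

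**The case against.** The strongest reply is that 11.1 is a list of variables and types, not the questionnaire. The logistics ratings are collected in the Participation Questionnaire, whose items are not in the documents, so branching or a not-applicable choice cannot be excluded. The list also cannot be meant as a full grid for everyone, since no patient has the ELISA test; respondents presumably rate only the tests they had. Section 5.3 says fields are required where appropriate, not always. This stands as far as size goes: actual distortion is not shown. It does not clear the plan, because POC remains in the list rated on shipping and storage, and no denominator rule is given.

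A reader might go further than the documents allow in four ways.

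- **That skipped items depress survey completeness, capping it at 50% (40 of 80 patients).** Sections 3.0 and 11.1 do not list the Participation Questionnaire among the forms measured for completeness. Section 13 speaks generally of analysing incomplete surveys and forms, and completing the study is not defined. Even if the questionnaire were counted, only that form would be affected, and no figure can be derived.
- **That POC will look easier than LAB.** This needs the five items averaged into one score and a comparison between test types. Section 11.1 plans neither; it gives frequencies.
- **That a primary outcome is affected.** Section 3.0 does not rank the ease and understandability ratings, and section 4 names willingness and protocol completion as the important outcomes.
- **That the separate LAB saliva and PCR rows are an error.** Section 7.2.1 distinguishes the DHCW PCR test, by saliva and/or tongue brush, from the patient LAB test, so two rows can be read as two procedures.

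**Conclusion.** Two mismatches hold on the face of the plan. First, POC is rated on shipping preparation and specimen storage, which 7.2.2 says do not apply to it. Those POC percentages have no meaning, and up to 40 POC patients have no shipped specimen at all. If results are tabulated by test, the problem stays there. If they are pooled, the summary can be distorted by an unknown amount; the ranges above are bounds that assume enrolment at the caps (for patients, equal numbers in POC and LAB offices) and no branching. Second, a respondent with mild difficulty on a self-administered survey has no truthful middle answer. This is most secure for the pre-visit survey, weaker for surveys done in the office, and absent for the Triage Survey.

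Priority is minor. The plan sets no sample size calculation, threshold or hypothesis test that depends on these ratings.

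**What to change.** - Restrict the shipping and storage items to shipped specimens, by branching on the tests the respondent had. Alternatively, add a not-applicable category and exclude it from the denominator.
- State in 11.1 that ease is reported by test, each with its own denominator. At the caps, shipping preparation would then rest on 40 LAB patients, 20 LAB DHCWs for PCR and 40 DHCWs for ELISA.
- For self-administered surveys, replace the middle understandability option with one that needs no administrator, for example: understandable after re-reading. Keep the current wording for the Triage Survey.
- For the Triage Case Report, have the person who enters it rate ease of administration, and keep the respondent's rating of whether the questions were understandable. Align 3.0 with this.

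The cost is edits to REDCap option lists and branching, and a few lines in 3.0 and 11.1. The one downside is slightly less comparability with the earlier feasibility study mentioned in section 5.2, if it used the same scales; the documents do not say whether it did.

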12 SOURCE DOCUMENTS AND ACCESS TO SOURCE DATA/DOCUMENTS

All study survey information will be captured electronically and stored on secure, encrypted Rutgers University servers.

- Patient consents will be captured and recorded directly into the REDCap system.
- All Patient and DHCW surveys will be recorded directly into REDCap via the following REDCap forms:

DHCW Participants	Patient Participants
Start-of-Study DHCW Survey	Triage Case Report
Triage Survey Case Report	Pre-Visit Patient Survey
End-of-Study DHCW Survey	End-of-Visit Patient Survey
DHCW Feasibility Study Participation Questionnaire	Patient Feasibility Study Participation Questionnaire
Testing Case Report	Testing Case Report

- Testing results will be captured in the REDCap Testing Case Report in the following ways:

	POC	PCR	ELISA
Original Source Document	N/A – Results appear on BD Veritor Screen or Abbott COVID-19 antigen test card and directly recorded into REDCap	Excel Spreadsheet posted onto SDM PREDICT box drive	Excel Spreadsheet posted onto SDM PREDICT box drive
Storage of Original Source Document	Not Applicable	Electronically stored on Rutgers server	Electronically stored on Rutgers server
Responsibility for Entering into REDCap	National Dental PBRN Practitioner or their investigator designee	Rutgers PI, Clinical Protocol Chief or their designee	Rutgers PI, Clinical Protocol Chief or their designee
Verification of Correct Entry into REDCap	Not Applicable	PI or Chief of Clinical Protocol or their designee	PI or Chief of Clinical Protocol or their designee

- At the end of the study, deidentified data will be provided to the National Coordinating Center.

All paper-based study source documents will be maintained in the Rutgers School of Dental Medicine Clinical Research Center which is located on the D Level of the Dental School Building. All documents will be secured in a locked file cabinet in the center. Access to the Clinical Research Center is limited to research center personnel via a card reader.

Study staff will maintain appropriate medical and research records for this study, in compliance with ICH E6, Section 4.9 and regulatory and institutional requirements for the protection of confidentiality of participants. Study staff will permit authorized representatives of NIDCR and regulatory agencies to examine (and when required by applicable law, to copy) research records for the purposes of quality assurance reviews, audits, and evaluation of the study safety, progress, and data validity.

